Protocol: A randomized controlled trial of three prophylactic antibiotic regimens for first trimester surgical abortion

NCT02756403

June 26, 2015

A randomized controlled trial of three prophylactic antibiotic regimens for first trimester surgical abortion

Fellow: [name]

Primary Mentor: [name] MPH

Additional Mentors: [name] MPH; [name] MPH

Fellowship Site: Washington Medstar Hospital

Date of initial proposal submission: January 2015

PROJECT SUMMARY

Justification for the project

Preoperative oral antibiotics have been shown to decrease infection rates for surgical abortion, and are universally recommended by the Society of Family Planning ¹. While data shows that that several different drug regimens appear to be effective in preventing perioperative infection,² we do not currently have data comparing side effects and patient tolerability of these various regimens. Data does suggest higher rates of nausea with doxycycline versus placebo,³ but we lack sufficient evidence to recommend any one medication over another. Azithromycin 500 mg, doxycycline 200 mg, and metronidazole 500 mg are recommended for use before abortion by Planned Parenthood and the National Abortion Federation, and have been widely adopted since the previously most commonly used regimen (doxycycline 200 mg twice daily for 7 days post-procedure) became unreasonably expensive. Prior to doxycycline price increase, the standard of care had been post-procedure prophylaxis.

Proposed research

This double-blinded randomized controlled trial will consist of 180 participants undergoing first-trimester surgical abortion. Each subject will be randomized to one of four groups:

1. Azithromycin 500 mg – single dose
2. Doxycycline 200 mg – single dose
3. Metronidazole 500 mg – single dose
4. Placebo (with post-procedure antibiotics: azithromycin 1 g once or doxycycline 200 mg twice daily for 7 days)

The primary outcomes are nausea, vomiting, and pain. Subjects will be assessed for the presence of these symptoms before administration of study drug, immediately following the abortion procedure, and again in the recovery area.

A substudy will assess for serum drug levels and for the presence of viable bacteria within the endometrial cavity in 40 women.

New features

This will be the first study to compare side effect profile and patient tolerability for the three most commonly used prophylactic antibiotic regimens for first-trimester surgical abortion.

The substudy will be the first to examine the use of bacterial cultures from the endometrial cavity after abortion. If performing bacterial cultures is found to be useful, further studies will be warranted to evaluate this method as a potential surrogate for efficacy. An earlier landmark study by Mishell et al. employed culture of the endometrial cavity associated with use of intrauterine devices.⁴

Problems anticipated

No major problems are anticipated in the main study. Six months should be sufficient for enrollment, as both project sites have high volumes of first-trimester surgical abortions.

For the pilot substudy, the anticipated findings are unclear. We intend to establish the methods to make cultures of the endometrial cavity a useful tool for use in future studies of antibiotics at abortion.

1.1 Rationale and objectives of the study

1.1.1 Rationale

Preoperative antibiotic prophylaxis has been proven effective in preventing infection in patients undergoing surgical abortion in multiple placebo-controlled studies.⁵ All antibiotics given prior to abortion have been found to be effective in reducing infections. However, at present, published comparative data do not address side effects with various antibiotic regimens. Accordingly, from the perspective of side effects, clinicians cannot recommend any one agent over the others.

Anecdotally, doxycycline and metronidazole appear to be associated with higher levels of gastrointestinal side effects, including emesis. Patient experience and satisfaction may also be negatively impacted by a medication that has a higher rate of unpleasant side effects. If we are able to demonstrate a significant difference in side effect profiles and/or patient satisfaction for the study medications, then we may be able to improve patient experience.

Our substudy will examine endometrial bacterial culture following first-trimester surgical abortion, using samples collected by suction endometrial biopsy. A 2014 study that examined bacterial ecology in the vagina, cervix, and uterus did not show a significant change in bacterial species identified by PCR before and after levonorgestrel IUS insertion.⁶ Predominant species were genus *Lactobacillus* and *Burkholderia*.⁶ Since we are only interested in the types and amount of living bacteria, we will use a culture method (instead of PCR) for both anaerobic and aerobic species. As this will be performed after the completion of the procedure (involving multiple passes in and out of the cervix), we expect the cervical and uterine microbiota to be essentially the same.⁴ Thus we do not plan to use a protective sheath over the endometrial biopsy device cannula.

1.1.2 Objectives and Hypotheses

This study aims to investigate the side effects of three different preoperative antibiotic regimens used for surgical abortion prophylaxis and a pre-operative placebo and to determine if any differences exist.

The primary objective is to determine if the side effects associated with individual medications are more similar to placebo than the others. We hypothesize that all study medications will cause more nausea than placebo. Primary outcome measures are nausea, emesis, and patient satisfaction.

We will assess pain in our questionnaires as a secondary study outcome. It is conceivable that the study interventions will alter pain perception either due to the influence of nausea or emesis on pain perception or, less likely, due to direct effects on perceived pain. We will note if the patient was in the endometrial assessment substudy as this may also affect pain perception.

The substudy aims to explore our ability to identify bacteria within the uterine cavity. The objective is to assess the feasibility of identifying bacteria within the uterus after abortion. We hypothesize that the

burden of bacteria will be higher in women receiving placebo, and that aerobic bacteria will not be decreased with metronidazole.

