1.3 Design and Methodology

1.3.1 Research Design and General Methodological Approach

Primary study: We have designed a randomized controlled trial to be conducted at Washington Hospital Center (WHC) and Planned Parenthood of Metropolitan Washington (PPMW) over the course of 6-8 months. A total of 180 English-speaking women will be enrolled with 45 participants in each of the four groups.

The women will be randomized to receive single oral doses of azithromycin 500 mg, doxycycline 200 mg, metronidazole 500 mg, or placebo. Computer-generated randomization will be used to assign participants to one of the four treatment arms. Women receiving placebo will receive antibiotic prophylaxis after completion of the study.

Both the participants and the investigators will be blinded as to the treatment group. This will be accomplished by placing the study medication inside opaque gelatin capsules, a method that has been successful in prior studies.³ We will randomize participants by assigning them to the next of the sequentially numbered sealed opaque study packets, containing the gelatin capsules with study medication inside. A second smaller opaque sealed envelope will also be inside the study packet. This envelope will be opened after completion of all study procedure and will only say if the participant received placebo, so that additional antibiotics can be given.

Participants will swallow the appropriate medication approximately 30-60 minutes prior to the surgical abortion. We will assess side effects via written questionnaire immediately before the start of the procedure and in the recovery room. Study population will be all eligible patients undergoing surgical abortion in the first trimester at PPMW and at WHC.

For the substudy 40 women will be recruited to undergo immediate post-procedure endometrial sampling using a suction-piston device. Due to the double-blind nature of this study, enrollment into the substudy will not be by group. Thus there are likely to be unequal group sizes. For a pilot substudy such as this, unequal numbers within groups will not detract from the utility of the results.

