1.3.2 Criteria for selection of participants

We will enroll up to 200 women so that 180 women complete the final post-procedure questionnaire. We will enroll women who meet the following criteria (see Appendix H):

- Women in good general health
- Age 18 or over
- Seeking non-urgent surgical termination of pregnancy
- Gestational age of 5 0/7 to 13 6/7 weeks, confirmed by sonography
- English-speaking

Women who meet any of the following criteria will be excluded:

- Early pregnancy failure or fetal demise
- Intolerance, allergy, or contraindication to any of the study medications
- Inability to tolerate oral intake due to current nausea or vomiting
- Desire to use intravenous sedation.

For the substudy, women will be recruited until 40 samples have been obtained. The only inclusion criterion is eligibility for the main study. We will exclude women from the substudy if procedural complications such as perforation or hemorrhage occur that would make endometrial sampling unsafe or inadvisable.

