The patient will only open the randomization packet at take the study medication at the time of pre-medication for her abortion procedure. She will hand the small envelope to the research staff. The allocation number will be recorded twice on the participant's chart. At the time of allocation, the small envelope will be attached to the participant's chart, and will be opened by the PPMW or WHC staff after collection of the final post-procedure questionnaire. If the participant is in the placebo group, appropriate post-procedure antibiotics will be given, such as azithromycin 1 g or doxycycline 100 mg twice daily for 3 days.

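### The Project Summary and the body disagree on the primary outcomes and the middle assessment; the body itself sets no lead outcome, primary time or error control

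*Combined protocol and SAP*

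**What the plan says.** **Outcomes.** The Project Summary states: "The primary outcomes are nausea, vomiting, and pain". Section 1.1.2 states: "Primary outcome measures are nausea, emesis, and patient satisfaction", and adds: "We will assess pain in our questionnaires as a secondary study outcome". Its only hypothesis for the main study is: "We hypothesize that all study medications will cause more nausea than placebo".

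**Timing.** The Summary places the two assessments after dosing "immediately following the abortion procedure, and again in the recovery area". Section 1.3.1 states: "We will assess side effects via written questionnaire immediately before the start of the procedure and in the recovery room". Section 1.3.6 and the title of Appendix D agree with 1.3.1.

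**Analysis.** For the recording of the primary outcomes, section 1.3.10 refers to 1.1.2, 1.3.1 and 1.3.5. It leaves the choice between parametric and non-parametric methods open. It names no lead outcome, no primary time and no multiplicity rule. Section 1.3.11 derives 45 women per group from a 30% difference from placebo in one unspecified outcome, with 80% power and alpha 0.05.

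**The concern.** Vomiting and emesis are the same outcome, so the conflict over outcomes concerns pain and satisfaction. Pain is primary in one place and secondary in another. Satisfaction is primary in one place and absent from the other. The middle assessment also moves from one side of the procedure to the other.

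Settling that conflict in favour of the body still leaves the primary result undefined. The pre-procedure score reflects the study drug and premedication alone, whereas the recovery score also follows the paracervical block and the aspiration. The same drug could look different from placebo at one time and not at the other. With three outcomes, two times and three drugs against placebo, the result reported as primary could be settled after the data have been seen, and the stated alpha of 0.05 would not describe the trial's error rate.

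**Working it through.** **1. Which text is operative.**

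| Item | Project Summary | Body |
|---|---|---|
| Pain | primary | secondary (1.1.2) |
| Satisfaction | not listed | primary (1.1.2) |
| Middle assessment | after the procedure | before it (1.3.1, 1.3.6, Appendix D title) |

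Section 1.3.10 cites body sections only. No precedence rule is written, but the body is the natural reading.

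**2. Whether the body names a primary time.** Two hints point in opposite directions. Section 1.3.2 counts completers at the last questionnaire: "We will enroll up to 200 women so that 180 women complete the final post-procedure questionnaire". Section 1.3.6 ties the primary outcomes to the pre-procedure questionnaire and then says that the final one assesses the study outcomes again. Neither settles the matter.

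**3. The plan's own figure.** The placebo rate and the number of sides are not stated. Assume a two-sided test, 30% read as percentage points, and 20% on placebo against 50% on a drug (mean 0.35).

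- Uncorrected: n = [(1.960√(2·0.35·0.65) + 0.842√(0.20·0.80 + 0.50·0.50)) / 0.30]² = [(1.322 + 0.539)/0.30]² ≈ 38.5, so 39.
- With continuity correction: (38.5/4)·[1 + √(1 + 4/(38.5·0.30))]² ≈ 44.9, so 45.

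The 45 per group is reproduced. It covers one outcome, one time and one contrast at an unadjusted 0.05. A relative 30% does not give 45 in a two-sided test (170 per group at a 50% placebo rate, 55 at 70%).

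**4. Number of drug-placebo tests.** At one time: 3 outcomes × 3 contrasts = 9. At both times: 9 × 2 = 18. The questionnaires appear only as titles. If satisfaction is asked only at recovery, the second count is (3 + 2) × 3 = 15, and the error rate lies between the two rows below.

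**5. Chance of at least one p < 0.05 if no drug affects any outcome.** Assumptions: two-sided tests, normal approximation, correlation 0.5 between contrasts (shared placebo group, equal groups), and a common correlation r among outcome-by-time scores. The documents give no r. Results are simulated.

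| Tests | r = 0 | 0.3 | 0.5 | 0.7 |
|---|---|---|---|---|
| 9 | 33.2% | 31.8% | 29.4% | 25.8% |
| 18 | 55.2% | 51.3% | 45.3% | 37.1% |

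One outcome at one time with three unadjusted contrasts still gives about 12.5%.

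**6. Power at 45 per group after adjustment.** Power = Φ[(0.30√45 − z√(2p̄(1−p̄))) / √(p₁(1−p₁) + p₂(1−p₂))], with 0.30√45 = 2.012.

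| Critical value z | 20% v 50% | 35% v 65% |
|---|---|---|
| 1.960 (unadjusted) | 86% | 82% |
| 2.348 (Dunnett, 3 contrasts) | 75% | 70% |
| 2.394 (Bonferroni, 3) | 73% | 68% |
| 2.773 (Bonferroni, 9) | 59% | 53% |

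Example, 35% v 65% with Bonferroni over 3: (2.012 − 2.394·0.707)/0.675 = 0.474, and Φ(0.474) = 0.68. A placebo rate of 35% gave the lowest unadjusted power of the rates tried (1% to 60%).

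**The case against.** The strongest reply has five parts.

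- **The body governs.** This stands for the contradiction, which needs only an alignment edit. It does not touch the gap, which lies wholly within the body.
- **The comparisons are evident.** This stands. Sections 1.1.2 and 1.3.11 frame the question against placebo. Section 1.7 mentions differences between drugs as an expected finding, not as an analysis. A reader might infer that no comparison set exists at all. The narrower point is that the status of drug-drug comparisons is unstated.
- **Two assessments need not mean two tests.** This stands as a remedy. Baseline symptoms are recorded (1.3.5), and so is emesis during the procedure (1.3.6), so a single combined analysis is possible. The plan does not specify one.
- **The error rates are a worst case.** Partly right. The upper ends need uncorrelated scores in the same woman, and every figure assumes no drug effect, although 1.1.2 expects all the drugs to increase nausea. Treating every test as independent gives 1 − 0.95⁹ = 37% and 1 − 0.95¹⁸ = 60%; those figures ignore the shared placebo group and should not be used.
- **This is a small tolerability trial, and adjustment across distinct drugs is debated.** Fair as an argument about which rule to choose. It does not excuse stating none, because the plan sets alpha at 0.05 and 1.7 looks to significant differences to inform the choice of drug.

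**Conclusion.** The concern holds. The Summary and the body conflict on pain, satisfaction and the middle assessment, and the body leaves the primary result undefined across 9 to 18 drug-placebo tests, each at 0.05. Under a global null the chance of a false positive is about 26-33% (one time) or 37-55% (both times). These figures rest on assumed correlations of 0.7 to 0 and are upper-end illustrations, because true effects on nausea would leave fewer true nulls. The gap should be closed before the trial's results can be read, since it cannot be credibly repaired once outcomes have been seen by group.

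Three stronger readings are not supported. The documents show that selecting a result is possible, not that it is intended. The 45 per group is not an arithmetic error. Nor is study-level unblinding missing as a milestone: 1.3.6 and 1.3.8 both refer to it, and the small envelope separates placebo from the rest without identifying the drugs. Even so, that envelope "will be opened by the PPMW or WHC staff after collection of the final post-procedure questionnaire", and 1.3.13 plans same-day data entry. A deadline tied to seeing outcome data by group is therefore the safer one.

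**What to change.** Before enrolment, or at the latest before outcome data are examined by group:

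1. Align the Project Summary with 1.1.2 on outcomes and with 1.3.1 and 1.3.6 on the schedule.
2. State how the two post-dose assessments form the primary result. Either name one time or specify one combined analysis, for example any emesis after dosing, and a baseline-adjusted repeated-measures analysis for nausea.
3. Name one lead outcome. Nausea is the candidate, as the only main-study outcome with a hypothesis. Make its drug-placebo contrasts primary, in a fixed sequence or with a Dunnett adjustment, and label the other outcomes and the drug-drug comparisons secondary.
4. Say which outcome, time and contrast the 45 per group refers to, and add 1.3.6 to the cross-reference in 1.3.10.

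**Cost.** These are text changes, and the visits stay as they are. The trial gives up freedom in choosing its primary result. With an adjustment it also loses some power: on the assumptions above, from 82-86% to about 70-75% with Dunnett over three contrasts, 68-73% with Bonferroni over 3, and 53-59% with Bonferroni over 9. A fixed sequence keeps the planned power for its first comparison, so no extra enrolment is needed. Its price is that each later comparison depends on the ones before it.

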1.3.6 Follow-up Procedure

Immediately prior to procedure (acceptable range 0-15 minutes) the participant will complete a questionnaire (Appendix D) assessing the primary study outcomes. Time of questionnaire completion will be recorded on the patient's chart and on the questionnaire itself. The abortion procedure will be performed in the usual fashion at that facility. The details of the paracervical block will be recorded by the abortion provider: volume, local anesthetic concentration, and other agents added. Episodes of emesis during the procedure will be recorded by the provider.

For the patients enrolled in the substudy, immediately after completion of the uterine aspiration but before removal of tenaculum, the endometrial sample will be collected. The external os will be cleaned with chlorhexidine. The physician investigator will pass the endometrial sampling device to the fundus and then withdraw the plunger to collect a sample at the fundus. If a second pass is needed to collect an adequate sample, a new sterile device will be used. The sample will be placed in appropriate medium for anaerobic and aerobic culture.

After completion of the procedure, substudy patients will have a blood sample collected via venipuncture before leaving the procedure room. This sample will be spun and frozen until the end of the study. After unblinding of the study data, the serum for each participant will be sent for the appropriate assay to determine the level of doxycycline, azithromycin, or metronidazole, as appropriate. No testing will be performed for participants receiving placebo.

Prior to discharge from the recovery room, the participant will complete a final questionnaire in the recovery area, again assessing the study outcomes (Appendix E). After completing the final questionnaire, the second envelope will be opened. Participants receiving placebo will be given azithromycin 1 g. If azithromycin is contraindicated, doxycycline 100 mg twice daily for 3 days will be given. Then participants will be given a \$50 gift card. Participants in the substudy will be given an additional \$50, for

\$100 in total.

Each participant will also receive a telephone call 1-2 weeks after the abortion procedure to assess for evidence of infection (Appendix F). Date and time of completion of all questionnaires will be recorded.

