1.3.10 Data Analysis

Data analysis will be conducted using Stata. The baseline characteristics of the populations will be described. Primary outcomes will be recorded as described above in 1.1.2, 1.3.1, and 1.3.5. Outcomes will be assessed using parametric or non-parametric analysis as appropriate.

The primary analysis will be based on intention-to-treat analysis, as participants will be analyzed based on the randomization group they are assigned regardless of actual treatment. Although study discontinuation after enrollment is possible, we expect extremely low discontinuation in this one-day study.

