1.3.11 Number of Subjects and Statistical Power

Sample size: 180 women for main study

To detect a 30% difference in a given outcome compared to the placebo group, we will need to enroll 45 women per group to achieve a power of 80% with alpha of 0.05.

For the endometrial sampling substudy, we will enroll 40 women. As this has not been done previously,

we cannot predict results with any accuracy. We expect that roughly 10 women per group will give us enough data to understand if this methodology will be fruitful for future research, without undue risk to a large number of women at this early stage. Enrollment in the sub-study may be more challenging but we need many fewer participants. To give a rough idea of power, the substudy will have 85% power with alpha of 0.05 to detect a reduction in positive culture (any bacteria detected) from 90% with placebo to 20% in a treatment group. This assumes 10 women per group.

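### Section 1.3.10 names no analysis that uses substudy status or pre-drug pain, which costs the recovery-room pain comparison a modest amount of precision

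*Combined protocol and SAP*

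**What the plan says.** - **Substudy and pain.** Section 1.1.2 states: "We will note if the patient was in the endometrial assessment substudy as this may also affect pain perception".
- **Timing of sampling.** Section 1.3.6 states that "immediately after completion of the uterine aspiration but before removal of tenaculum, the endometrial sample will be collected". Substudy women also have blood drawn before they leave the procedure room. Both come before the final recovery-area questionnaire.
- **Size and balance.** Section 1.3.1 plans 40 sampled women. It does not recruit them by arm and says that unequal numbers are likely. It accepts this for the pilot's own results and does not discuss main-study pain.
- **Order of consent.** Under section 1.3.5, substudy consent is signed before the randomization packet is assigned.
- **Status of pain.** The Project Summary says: "The primary outcomes are nausea, vomiting, and pain". Section 1.1.2 makes pain secondary.
- **Pre-drug pain.** The Project Summary has the primary symptoms assessed before study drug. Section 1.3.5 describes a baseline symptom survey and singles out nausea.
- **Analysis.** On method, section 1.3.10 says: "Outcomes will be assessed using parametric or non-parametric analysis as appropriate". It adds a baseline description and intention-to-treat. It names no covariate, stratification or sensitivity analysis.

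**The concern.** The protocol records substudy status for a stated reason, its possible effect on pain, and then does not say how the variable will be used. Forty of 180 women (22%) have an extra intrauterine pass and a venipuncture shortly before the last pain score, and their split over the arms is left to chance. If sampling hurts, it adds variation to recovery-room pain that has nothing to do with the drug, and an analysis without the variable leaves that variation in the standard error. The same holds for any pain present before the drug is taken.

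Because 1.3.10 is silent, the choice to adjust, and for which version of the variable, could also be made after the data are seen.

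**Working it through.** **1. The plan's own figure.** Section 1.3.11 gives the target as "To detect a 30% difference in a given outcome compared to the placebo group". Its stated answer is 45 per group, at 80% power and alpha 0.05. No placebo rate is given. With a 30-point absolute difference, two-sided alpha 0.05 and 80% power, 20% vs 50% needs 39 per group uncorrected and exactly 45 with continuity correction. Over all placebo rates the largest uncorrected requirement is 43 (35% vs 65%). So 45 reproduces as a comparison of proportions for an unnamed outcome. It is not tied to pain, and the power figures in step 5 are therefore illustrative.

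**2. Inputs.** From the documents: 45 per arm, four arms, 40 sampled, f = 40/180 = 0.222, f(1 - f) = 0.173. Assumed, because the documents give none of them: a 0-100 pain scale, SD 25 among women with the same substudy status, and a sampling effect δ between 0 and 20 points.

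**3. Chance imbalance.** Distribute 40 women at random over 4 × 45 (multivariate hypergeometric, 400,000 draws).

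| Gap in sampled share, drug vs placebo | Mean | More than 15 points |
|---|---|---|
| One given comparison | 7.0 points | 9.9% |
| Largest of the three comparisons | 11.0 points | 23.5% |

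The SD of the gap for one comparison is 3.95 women, or 3.95/45 = 8.8 points. A gap of 7 points shifts the pain difference by 0.07δ, which is 0 to 1.4 points. A gap of 15 points shifts it by 0.15δ, which is 0 to 3 points.

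**4. Standard error.** Adjusted: 25 × √(2/45) = 5.27 points. Unadjusted: √(625 + 0.173δ²) × √(2/45).

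| δ (points) | Added variance | Unadjusted SE | Increase |
|---|---|---|---|
| 0 | 0 | 5.27 | 0% |
| 5 | 4.3 | 5.29 | 0.3% |
| 10 | 17.3 | 5.34 | 1.4% |
| 15 | 38.9 | 5.43 | 3.1% |
| 20 | 69.1 | 5.55 | 5.4% |

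The added noise and the chance imbalance are one quantity. At δ = 20 the shift from imbalance has SD 20 × 0.088 = 1.76, and √(5.27² + 1.76²) = 5.56, which is the last row up to rounding. They must not be counted twice.

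**5. Power.** Take a difference that the adjusted analysis detects with 80% power: 2.80 × √(2/45) = 0.59 SD. Without adjustment, power is Φ(2.80/√v - 1.96), with v = 1 + 0.173(δ/25)².
- δ = 10: v = 1.028, power 78.9%.
- δ = 20: v = 1.111, power 75.8%, equivalent to 45 × 1.111 = 50 women per arm instead of 45.

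**6. Which assessments are exposed.** Under sections 1.3.1 and 1.3.6 the other post-dose questionnaire precedes the procedure, so only the recovery-room score follows sampling. The Project Summary instead places an assessment immediately after the procedure. The two schedules must be reconciled.

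**The case against.** The strongest reply is that this is one missing sentence in a short analysis section that names no model for any outcome. The protocol says only that participation may affect pain, and a parametric analysis can include covariates, so 1.3.10 does not exclude adjustment. The effect of sampling could be close to zero: it follows an aspiration done under oral analgesia and paracervical block, and the score is taken later, in recovery. All of this stands, and it is why the range starts at zero.

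A reader might infer more than the documents support:

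- **That the pain comparison is biased.** It is not. Substudy consent comes before packet assignment and is blind to arm. Chance imbalance is already reflected in the unadjusted standard error, so type I error is intact.
- **That the protocol expects an effect, or commits to an unadjusted analysis.** It says neither.
- **That a gap above 15 points in 23% of trials is the typical risk.** That is the largest of three comparisons; for any one comparison it is about 10%.

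Two further objections shape the remedy. The pain scale is unknown, since the questionnaires are not available. If pain is yes/no, the SD-based figures do not apply, and adding covariates to a logistic model changes the odds ratio being estimated. Also, section 1.3.2 recruits until 40 samples are in hand, so consenters may exceed 40 and the consent term would then remove somewhat less variance than step 4 shows.

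**Conclusion.** The point holds as a modest, inexpensive gain in precision for recovery-room pain. Substudy status is recorded because of pain, pre-drug symptoms are to be assessed, and 1.3.10 uses neither. Under an assumed sampling effect of 0-20 points and SD 25, leaving out the substudy term makes the standard error about 0-5% larger and costs between nothing and about 4 points of power. If sampling has no effect on pain, that term gains nothing. The gain from the pre-drug score depends on its correlation with the final score, which the documents do not give, so it is not quantified here.

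The priority is low if pain is secondary, as in 1.1.2, and somewhat higher if it is primary, as in the Project Summary. That conflict has to be settled separately.

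**What to change.** Add to section 1.3.10:

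- Pain at the final questionnaire is compared between arms by a regression with treatment arm, pre-drug pain score and substudy consent (yes/no) as terms. The unadjusted comparison is reported as a sensitivity analysis.
- Substudy status means consent, which is fixed before the packet is assigned. It does not mean that a sample was obtained: sections 1.3.2 and 1.3.7 let women leave the substudy because of events during the procedure, after randomization.
- If pain is recorded as yes/no, the same covariates are used and an adjusted risk difference is reported, so that the estimand does not change.

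Confirm that the baseline questionnaire (Appendix C) asks about pain, since section 1.3.5 singles out only nausea.

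The cost is a few sentences and two model terms, each one degree of freedom out of about 176 (180 - 4). No extra women or visits are needed, and no new data if Appendix C already records pain.
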